#### *Audiologic examination*

An audiologic examination will be performed on all subjects at baseline and on all balloon dilation and crossover subjects at the 6-month follow-up.

Audiometry procedures should be conducted in compliance with the ANSI Method for Manual Pure-Tone Threshold Audiometry, ANSI S3.21-1978 (R1997). Computerized or self-recording audiometers should be used according to their manufacturer's instructions.

Pure tone (air-bone gap) audiometry testing will be performed using pulsed tones with the better ear, if known, tested first. The preferred frequency sequences for air and bone conduction measures are shown in **Table 2**. If masking is used, the type and level should be noted on the CRF. The air-bone gap will be calculated and reported on the CRF.

Table 2. Preferred Frequency (Hz) Testing Sequence for Air-bone Conduction Tests

Test Order	1	2	3	4	5	6	7
Air	1000	2000	4000	8000	1000 a	500	250
Bone	1000	2000	4000	1000 a	500		

a When testing the second ear, the repeat 1000 Hz test is not necessary before testing the lower frequencies.

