### 2.9.2 Baseline visit

All candidates for the study will have the following baseline clinical evaluations done **before enrollment and randomization**:

- Informed consent signed
- Baseline medical history, demographics, symptoms, and medication history in the 12-month period before enrollment
- Eligibility assessment: subjects meet all inclusion and no exclusion criteria.
- Nasal endoscopy
- Otoscopy examination
- Tympanometry
- Valsalva evaluation

- Assessment of ear infections over the 12-month period before enrollment
- Audiologic examination including a pure tone auditory (PTA) test
- EQ-5D and ETDQ-7 QOL questionnaires (completed by the study subject)
- Pregnancy test for female subjects of childbearing potential

The results of all baseline evaluations will be documented on the appropriate Case Report Forms (CRFs).

For subjects undergoing balloon dilation, preprocedure antibiotics and steroids may be prescribed at the discretion of the study physician. Medications may be prescribed to treat active infections and procedures may be rescheduled until active infections resolve.

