#### *Complication rate*

A complication is defined as a serious adverse event that is device-related or procedure-related as noted in **Section 6**. The parameter of interest is the percent of subjects who experience 1 or more complications from the time of the index procedure through the 6-month follow-up.

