### 3.2 Potential risks

Study subjects will be informed of all known potential side effects and complications associated with study treatment and study assessments before consenting for the study. The risks associated with participating in the study are the same as those that the subject would have if treated with transnasal Eustachian tube balloon dilation outside of the study. These potential risks include:

- Complications from anesthesia
- Pain
- Bruising and swelling
- Bleeding
- Infection
- Continued or worsening symptoms
- Revision surgery
- Tinnitus
- Preauricular emphysema
- Damage to the ET
- Patulous ET
- Permanent hearing loss
- Tympanic membrane damage
- Carotid artery damage
- Cerebrospinal fluid leak

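### The air-bone gap is the only audiometric result the plan calculates; used alone, it could miss a sensorineural or high-frequency hearing loss after dilation

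*Combined protocol and SAP*

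**What the plan says.** The Audiologic examination part of section 2.10.2 sets the timing: "An audiologic examination will be performed on all subjects at baseline and on all balloon dilation and crossover subjects at the 6-month follow-up". Table 1 schedules no audiogram at the crossover evaluation, 6 weeks, 3 months or 12 months, so the 6-month audiogram is the only one after the procedure.

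The test is described by the gap itself: "Pure tone (air-bone gap) audiometry testing will be performed using pulsed tones with the better ear, if known, tested first". Table 2 gives the frequencies in test order. For air conduction the row reads "Air 1000 2000 4000 8000 1000 a 500 250", and for bone conduction "Bone 1000 2000 4000 1000 a 500". One derived value is named: "The air-bone gap will be calculated and reported on the CRF".

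No section asks for a change in air or bone threshold, a pure-tone average or a criterion for threshold shift. The abbreviation in section 2.9.2, "Audiologic examination including a pure tone auditory (PTA) test", refers to the test and not to an average. Section 2.9.2 also sends the results of all baseline evaluations to the CRFs. Audiometry is one of the other measures of section 2.10.2, and section 2.7 gives it no analysis of its own.

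Section 3.2 lists "Permanent hearing loss" as a potential risk. The primary safety endpoint is narrower: "A complication is defined as a serious adverse event that is device-related or procedure-related", counted through 6 months (section 2.10.1).

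**The concern.** The plan tests hearing before and after the procedure and lists permanent hearing loss as a risk, yet the one value it asks sites to calculate describes the difference between two thresholds and not the level of either. The gap isolates the conductive (middle-ear) part of a loss. That is a reasonable thing to track for a treatment meant to improve middle-ear pressure equalization (section 1.1), but it is the wrong lens for an inner-ear injury, which raises both thresholds.

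The two effects can also occur together. If middle-ear function improves while the inner ear is harmed, the gap narrows and the ear looks better on the only calculated measure.

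At stake is how much the 6-month safety data can say about hearing. Section 1.2 states that these data are to support a 510(k) application. Control subjects have no repeat audiogram unless they cross over and are dilated, so the within-ear change from baseline to 6 months is the only audiometric evidence on the question.

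**Working it through.** **Inputs from the documents**
- Air-conduction frequencies (Table 2): 250, 500, 1000, 2000, 4000 and 8000 Hz.
- Bone-conduction frequencies (Table 2): 500, 1000, 2000 and 4000 Hz.
- Derived result (section 2.10.2): the air-bone gap. No formula is given. I take gap = air threshold minus bone threshold, averaged over the frequencies that have both.
- The audiometry section states no figure of its own to reproduce, and the sample size does not depend on it.

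**Formula**

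Change in gap = change in air minus change in bone. Three consequences hold at any threshold level:
1. If air and bone both worsen by x dB, the change is x − x = 0.
2. If bone worsens more than air, the change is negative and reads as improvement.
3. Only a worsening of air that exceeds that of bone widens the gap.

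**Illustration**

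The documents give no thresholds. The values below are assumed: air 25 dB and bone 10 dB at each shared frequency at baseline, so the gap is 25 − 10 = 15 dB.

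| Case | Air at 6 months (dB) | Bone at 6 months (dB) | Gap at 6 months (dB) | Change in gap (dB) |
|---|---|---|---|---|
| (a) Both worsen by 20 | 45 | 30 | 15 | 0 |
| (b) Air worsens by 10, bone by 20 | 35 | 30 | 5 | −10 |
| (c) Both worsen by 30, at 4000 Hz only (means shown) | 32.5 | 17.5 | 15 | 0 |
| (d) Air worsens by 15, bone unchanged | 40 | 10 | 30 | +15 |

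Case (d), a conductive loss, is detected. Cases (a) and (c) are invisible in the gap, and case (b) looks like a gain although both thresholds worsened. Case (c) also shows that a four-frequency average dilutes a focal loss: 30 dB at one frequency moves it by only 30/4 = 7.5 dB. Averages alone are therefore not a sufficient replacement.

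**Frequencies outside the gap**

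Air is tested at 250 and 8000 Hz, but bone is not. A loss confined to either frequency never enters the gap, whatever its size. The plan measures both and names no use for them.

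**Other routes to the same harm**
- Section 6.1 defines an adverse event broadly and includes an increase in severity of an underlying disease.
- Section 6.4 finds events by volunteered complaint, questioning or physical examination. It does not mention the audiogram.
- Muffled hearing, clogged ears and ringing are among the qualifying symptoms in section 2.8.1, so a new loss may be put down to the existing condition. The same symptoms are asked about at every follow-up visit through the ETDQ-7, which gives a noticed loss repeated chances to be recorded.

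**The case against.** The strongest reply is that the sentence on the gap is an instruction for completing a form, not an analysis plan. It does not say that only the gap is recorded, nor that the gap is the hearing-safety result. This is right, and it rules out several stronger readings.

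- *That the plan intends to conclude there was no hearing harm from the gap.* Section 2.7 plans no specific analysis of audiometry, so no such conclusion is laid down. What is shown is that the only value named could not support one.
- *That thresholds are not captured.* The gap cannot be calculated without them. Section 2.9.2 sends baseline results to the CRFs, and section 2.10.2 wants masking type and level noted there, so the form holds more than the gap. The CRFs are not among the documents, and threshold fields may exist. But section 2.9.2 covers baseline only and does not itemize frequencies.
- *That the loss is hidden from the investigator, or the subject's care harmed.* The site performs the audiogram and holds the thresholds. The documents do not support this reading.
- *That the primary complication rate is understated.* A complication must be a serious event related to the device or procedure. A shift that the subject has not noticed might not be judged serious, so better reporting could leave the rate unchanged.

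It is also fair that adverse-event questioning and symptom visits give partial cover, and that the decibel examples are invented with no indication of how often such cases occur.

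What stands is the arithmetic, and the absence of any stated measure of threshold change at the one audiogram after dilation.

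**Conclusion.** The point holds in limited form. The gap is the only audiometric result the plan says to calculate. By construction it shows no change for an equal air and bone loss of any size, shows apparent improvement when bone worsens more than air, and excludes 250 and 8000 Hz. Used alone, it could miss the sensorineural or high-frequency form of a risk that the protocol itself lists.

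The size is qualitative: the direction of each error is certain, but the frequency is unknown because the documents give no thresholds or expected rates. A miss is possible, not certain, and an effect on the primary complication rate is not shown. The conclusion assumes that the gap is air minus bone, and that no unseen CRF or other document already specifies a threshold-change summary. It should be corrected because the data are already being collected, but it does not threaten the primary efficacy comparison.

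**What to change.** In section 2.10.2:
1. State that air and bone thresholds are recorded on the CRF for each ear and frequency, at baseline (before the procedure) and at 6 months. For crossover subjects, say that the comparison is with the enrollment audiogram, since Table 1 schedules no other before dilation.
2. Report the baseline-to-6-month change per treated ear in bone conduction (500 to 4000 Hz) and air conduction (250 to 8000 Hz), by frequency as well as averaged, alongside the air-bone gap. Keep the gap as the conductive measure.
3. List the ears whose bone or air thresholds worsened, with the size of each change, so that the investigator reviews them under the existing adverse-event definitions in sections 6.1 and 6.4. A numerical cut-off is not needed for this step.

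The cost is a few CRF fields, if they are not already there, and one extra table. Both thresholds are already tested under Table 2, so no new test, visit or subject is required and the sample size is unchanged.

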## 3 Risk/Benefit Analysis

### 3.1 Benefits

Participation in this study is voluntary; however, information gathered from this study will be used to apply for FDA clearance of a new indication for the XprESS device for Eustachian tube dilation. Subjects with ETD may experience an improvement in their symptoms.

### 3.2 Potential risks

Study subjects will be informed of all known potential side effects and complications associated with study treatment and study assessments before consenting for the study. The risks associated with participating in the study are the same as those that the subject would have if treated with transnasal Eustachian tube balloon dilation outside of the study. These potential risks include:

- Complications from anesthesia
- Pain
- Bruising and swelling
- Bleeding
- Infection
- Continued or worsening symptoms
- Revision surgery
- Tinnitus
- Preauricular emphysema
- Damage to the ET
- Patulous ET
- Permanent hearing loss
- Tympanic membrane damage
- Carotid artery damage
- Cerebrospinal fluid leak

### 3.3 Risk mitigation

The protocol has been developed to minimize the risks for the subject in a number of ways. Sample size was calculated to expose the smallest number of subjects while still being able to adequately test the study objectives. The subject selection criteria were designed to minimize risk by excluding patients who have comorbidities or conditions that may put the patient at higher risk for the balloon dilation procedure. Concomitant procedures that could increase risk and confound study results are not permitted during the study. The subjects are closely monitored by frequent follow-up visits during the study. Finally, the selected investigators are experienced in endoscopic surgery, specifically trained on use of the XprESS device, and expected to comply with the manufacturer's IFU for the XprESS device for Eustachian tube dilation.

## 4 Device Information

### 4.1 Investigational device description

The device under investigation in this study is the XprESS Multi-Sinus Dilation System (XprESS device). The device is currently a Class I, 510(k)-cleared, commercially available device for balloon sinus dilation.

The XprESS device combines features of a curved suction tip and an ostium seeker with the tissue expansion effect of balloon dilation. The features of this device enable a physician to track the device to the Eustachian tubes using endoscopic visualization. The distal end of the device is re-shapeable, allowing easy access to the Eustachian tubes. The XprESS curved suction tip has an atraumatic ball tip. A suction tube may be connected to the proximal barbed fitting to provide active suction by covering the suction vent. The XprESS balloon is available in diameters of 3-5 mm and in lengths of 8, 18, and 20 mm. All sizes are appropriate for treating Eustachian tubes; selection is based on physician preference. The XprESS device is provided sterile and for single use only.

### 4.2 Anticipated changes in device design

Changes to the device during the course of the IDE study are not anticipated. If such changes occur, Entellus Medical will inform investigators and will submit the appropriate supplemental applications to FDA, as necessary.

### 4.3 Investigational device management

Entellus Medical will control the use of the investigational devices by the following activities:

- Shipping or hand-carrying devices only to approved investigators who are participating in the study
- Maintaining records of shipment and distribution of the devices
- Maintaining records of devices used on subjects and returned devices

### 4.4 Device malfunctions

A device malfunction is defined as a failure of a device to meet its performance specifications or otherwise to perform as intended. A malfunction may be a result of any of the following: failure, malfunction, improper or inadequate design, manufacturing, labeling, or user error.

All device malfunctions must be reported on the Device Malfunction CRF. All attempts should be made to return malfunctioning devices to Entellus Medical for evaluation. Contact the clinical monitor for instructions on used device preparation and return procedures.

## 5 Monitoring Procedures

Entellus Medical personnel or qualified designees will monitor the clinical study in a manner consistent with 21 CFR 812, Subpart C, Responsibilities of Sponsor.

### 5.2 Investigators

The clinical monitors will ensure investigators are selected based on their qualifications and ability to fulfill the investigator responsibilities. Investigator qualifications and responsibilities are outlined in the Investigator Agreement that each investigator must sign before enrolling subjects in the study. An updated list of investigators and Institutional Review Boards (IRBs) will be provided to the FDA every 6 months during the study, or as otherwise requested.

### 5.3 Investigational center monitoring

Monitoring visits to the investigational centers will be conducted frequently during the study to ensure that all aspects of the current approved protocol and any amendment(s) are followed. Source documents will be reviewed for verification with data on the CRFs and all regulatory documents will be checked for accuracy including but not limited to IRB approvals, study-related correspondence, and subject informed consent. The investigator and/or investigational center staff must be available to meet with the sponsor during monitoring visits.

Upon reasonable notice, the investigator and institution agree to provide the sponsor representatives or designees and applicable regulatory authorities with direct access to source documents relevant to the study for sponsor quality assurance audits or inspections by the regulatory authorities.

## 6 Adverse Event Definitions and Reporting

### 6.1 Adverse events

An adverse event (AE) is any undesirable clinical occurrence experienced by the subject during the follow-up period regardless of the event's relationship to either the study device or the procedure. An underlying disease that was present at the time of enrollment is not an AE; however, any increase in the severity of an underlying disease is an AE. All adverse events will be reported to FDA in annual progress reports.

Microtears (<5 mm) of the ET mucosa after balloon dilation in the absence of other undesirable effects are not considered adverse events. It is hypothesized that the microtears are related to the mechanism of action and are critical to the tissue healing and remodeling of the ET after balloon dilation.

### 6.2 Serious adverse events

A serious adverse event (SAE) is an event that results in any of the following:

- Death
- Life-threatening
- Hospitalization or prolongation of an existing hospitalization
- Invasive surgical intervention to correct or prevent further injury
- Persistent or significant disability or incapacity
- An important medical event

An important medical event that may not meet one of the above definitions might be considered as an SAE if it jeopardizes the health of the subject or requires surgical intervention to prevent one of the outcomes listed in the above definition. An example of an important medical event is postoperative bleeding that requires an intervention such as cautery or additional packing but does not require hospitalization.

An elective hospitalization/intervention that was planned before the subject enrolled in the study is not considered an SAE as defined above.

### 6.3 Unanticipated adverse device effects

As defined in the IDE regulation 21 CFR 812.3, an unanticipated adverse device effect (UADE) is any serious adverse effect on health or safety, or any life-threatening problem or death caused by, or associated with, a device, if that effect was not previously identified in nature, severity, or degree of incidence in the protocol, subject informed consent form, or application, or any other unanticipated serious problem associated with a device that relates to the rights, safety, or welfare of subjects.

### 6.4 Assessing, recording, and reporting AEs, SAEs, and UADEs

An AE may be volunteered spontaneously by the subject or discovered as a result of questioning or physical examination by the investigator or study staff. The following information should be

reported for all AEs as soon as the investigator becomes aware of the event and updated as needed until the event resolves:

- Date the AE occurred
- Date the investigator (or staff) became aware of the AE
- Description of the AE (main complaints or symptoms)
- Relationship to the study device
- Relationship to the study procedure
- Seriousness
- Interventions undertaken
- Status of the AE

Source documents (eg, procedural notes, treatment notes, clinical summary) may be required as supporting documentation for an AE, SAE, or UADE.

During the study, all subject deaths must be reported to the sponsor within 24 hours of the investigator's (or designated staff's) knowledge of the death. Deaths should be reported on the End of Study CRF and the event leading to the death reported on an AE CRF. A copy of death records, medical records for the event(s) that led to the subject's death, death certificate (if available), and an autopsy report (if performed) should be deidentified and sent to the sponsor as soon as they become available.

## 7 Protocol Deviations

Investigators are required to adhere to the study protocol, signed Investigator Agreement, applicable national or local laws and regulations, and any conditions required by the applicable IRB or regulatory authority.

A protocol deviation is used to describe situations in which the protocol was not followed (including all required activities at each scheduled visit or activities occurring outside of the study windows). All attempts should be made to obtain sponsor approval for deviations before their occurrence.

An investigator must notify the sponsor and the applicable IRB of any deviation from the study protocol done to protect the life or physical well-being of a subject (medical emergencies). Such notice should be given within 24 hours. The sponsor will determine if the subject affected is eligible to continue in the study.

Documentation of deviations identified by the investigational center, the monitor, or other sponsor representative(s) will be entered onto the Protocol Deviation CRF for the purpose of tracking compliance with the protocol. The investigational centers will be required to document actions taken to prevent recurrence of deviations. The sponsor representative will initiate corrective actions based on individual deviations or trending reports, as appropriate.

## 8 Labeling

Entellus Medical will modify the existing FDA-cleared labeling (package labels and IFU documents) for the XprESS device to include the required investigational device statement (below), the indication statement, risks, and treatment procedure specific to Eustachian tube dilation.

The following statement will be included on the outer packaging unit and the IFU as required by 21 CFR 812.5:

- CAUTION-Investigational Device. Limited by Federal (or United States) law to investigational use.

## 9 Administrative Information

### 9.1 Investigational center selection

The study will be conducted at up to 7 investigational centers in the US. Centers will be evaluated to ensure each center has the capacity and capability to obtain informed consent and comply with all protocol requirements. The investigators and investigational center personnel are required to comply with the principles of Good Clinical Practices (GCP) as described in the FDA regulations.

### 9.2 Training

The training of investigational center personnel will be the responsibility of the sponsor or sponsor-authorized representatives. All treating physicians must be proficient in the use of endoscopic techniques. All physicians will be trained on the preparation and use of the XprESS device before subject enrollment in this study.

To insure uniform data collection and protocol compliance, the sponsor or sponsor-authorized representatives will review all components of the study with the study coordinator(s)/study staff at each investigational center. The review will include the study protocol, techniques for the identification of eligible patients, instructions for data collection during the procedure, and schedules for follow-up.

